#### 4.1.2 Exclusion Criteria

An individual who meets any of the following criteria will not be enrolled in the study:

1. Participant is female and has a positive pregnancy test result at screening.
2. Participant is female and is breastfeeding or will (re)start breastfeeding from the study vaccination to 3 months after vaccination.
3. Has an acute febrile illness with temperature  $\geq 38.0^{\circ}\text{C}$  or  $\geq 100.4^{\circ}\text{F}$  within 72 hours before study vaccination. Individuals with suspected COVID-19 symptoms should be excluded and referred for medical care.
4. Has a history of documented SARS-CoV-2 infection or COVID-19 within 6 months before screening.
5. Has a documented medical history of HIV, hepatitis B or hepatitis C infection prior to screening, or a positive test for these conditions at screening.
6. Any confirmed or suspected immunosuppressive or immunodeficient condition resulting from disease (eg, malignancy) or immunosuppressive/cytotoxic therapy (eg, medications used during cancer chemotherapy, organ transplantation or to treat autoimmune disorders). Chronic use (more than 14 continuous days) of any medication that may be associated with changes in immune function including, but not limited to, systemic corticosteroids exceeding 10 mg/day of prednisone equivalent, allergy immunotherapy injections, immunoglobulin, interferon, immunomodulators, cytotoxic drugs, or other similar or toxic drugs within 6 months of the first study vaccination. Inclusion of persons who use low dose topical, ophthalmic, inhaled, or intranasal steroid preparations is permitted.
7. History of myocarditis, pericarditis, or idiopathic cardiomyopathy, or presence of any medical condition that increases risk of myocarditis or pericarditis, including cocaine abuse, cardiomyopathy, endomyocardial fibrosis, hypereosinophilic syndrome, hypersensitivity myocarditis, eosinophilic granulomatosis with polyangiitis, persistent myocardial viral infection (eg, due to enterovirus or adenovirus), and celiac disease.

8. Has a new onset, clinically significant, abnormal biochemistry or hematology finding (defined as  $\geq$ Grade 1) at screening (adults with Grade 1 laboratory abnormalities that have been stable for at least 6 months before enrollment may be included in the study).

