2.1. Primary Objective and Endpoints

Objectives	Endpoints
Primary – Safety	
To evaluate the safety and tolerability of CV0501 at each dose level	
 Percentage of participants with each solicited local and systemic AEs during 7 days after vaccination (i.e., the day of study vaccination and 6 subsequent days (day 1 through 7) Percentage of participants with each abnormal clinical safety laboratory finding for 8 days after study vaccination Percentage of participants with unsolicited AEs for 28 days after study vaccination Percentage of participants with MAAEs, AESIs and SAEs from study vaccination through the end of the study (for 180 days after the study vaccine administration), each summarized separately

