3.4. Dose Adjustment/Modifications

An overdose is any dose of study vaccine given to a participant that exceeds the planned dose for an individual within a given dose group.

There is no specific treatment recommended for an overdose. Overdose itself is not to be reported as an adverse event (AE). Overdose participants will be included in the Safety Set and excluded from Per protocol Immunogenicity (PPI) Set.

4. General Statistical Considerations

Participants will be identified in the listings by the participant identification number concatenated with the site number. Data will be displayed in all listings sorted by age group, dose group and participant number.

Continuous data will be described using descriptive statistics (n, mean, standard deviation, median, minimum, and maximum).

Categorical data will be described using the participant count and percentage for each category.

For the **summary statistics** of all numerical variables unless otherwise specified, mean, confidence interval, median, standard deviation, minimum and maximum will be displayed.

A row denoted “Missing” will be included in count tabulations where specified on the shells to account for dropouts and missing values.

There is no formal hypothesis testing in this study where statistical methods are applied, the emphasis will be on estimation with 2-sided 95% Confidence intervals (CIs).

The denominator for all percentages will be the number of participants with non-missing values of corresponding parameter in that treatment within the analysis population of interest, unless otherwise specified.

A table, figure, listing (TLF) is to be generated for any required item even where no data is available or reported. In such cases, the table, figure or listing will state: “**No Data Reported**”. This will confirm to the health authorities that all data for the tables, figures, listings, and narratives are accounted for.

Baseline will be defined as the last non-missing evaluation prior to study vaccine administration, unless otherwise specified.

Study day will be calculated as follows:

- study day prior to the injection will be calculated as: date of assessment – date of the injection
- study day on or after the date of the injection will be calculated as: date of assessment – date of the injection + 1

For Safety assessment of AEs, the intervals will be calculated as follow

- solicited AEs: the day of vaccination and 6 subsequent days (day 1 through 7)

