- unsolicited AEs: the day of vaccination and 28 subsequent days (day 1 through 28)
- Medically attended adverse events (MAAEs), adverse events of special interest (AESI) and serious adverse events (SAEs): the day of vaccination and 180 subsequent days (day 1 through 180)

For calculations regarding antibody levels/titers, antibody results released as below a value will be replaced by $0.5 \times$ the value. Results released as above a value will be converted to the value. Missing results will not be imputed.

The lower limit of quantification (LLOQ) and upper limit of quantification (ULOQ) for WT NAb are the following:

LLOQ = To be defined by lab when assay calibrated.

ULOQ = To be defined by lab when assay calibrated.

calibrating conversion factor to WHO standard is 1/1.872.

NAb Result (IU/mL) = Result (NT50 titer) $\times 1/1.872$.

Details on LLOQs and ULOQs for IgG and conversion factors when available are described in Section 15.2

All safety data summaries/displays will be provided by dose group. Details will be included in the TLF shell.

All statistical analyses will be performed using SAS® software Version 9.4 or later.

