8.1. Analysis of Primary Safety Objective

8.1.1. Analysis of solicited local and systemic AE up to 7 days after study vaccination (day 1-7), unsolicited AEs up to 28 days after study vaccination (day 1-28), abnormal clinical safety laboratory finding up to 8 days after study vaccination (day 1-8) and non-serious Covid-19 adverse events (Day 1 – study end)

The percentages of participants with at least one solicited local or systemic AE for 7 days following vaccination (day 1-7), participants with unsolicited AEs up to 28 days after study vaccination (day 1-28), participants with abnormal clinical safety laboratory findings up to 8 days after study vaccination (day 1-8) and non-serious Covid-19 adverse events (day 1 – study end) will be computed by dose group.

8.1.2. Analysis of Medically attended Adverse Events (MAAEs), Serious Adverse Events (SAEs), and Adverse Events of Special Interest (AESIs) from study vaccination through the end of the study

Participants MAAEs and SAEs from study vaccination through the end of the study (approximately 180 days after the study vaccine administration, day 1-180) will be presented as the percentage of participants with such events throughout the study duration by dose and age group. Participants AESIs from study vaccination through the end of the study (day 1-180) will be presented by dose group.

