9.2 Clinical Laboratory Evaluations

The following laboratory assessments will be performed:

Hematology:	Basophils, eosinophils, erythrocytes (red blood cells), hemoglobin, leukocytes (white blood cells), lymphocytes, monocytes, neutrophils, and platelets
Chemistry:	Alanine aminotransferase, alkaline phosphatase, aspartate aminotransferase, total and direct bilirubin, blood urea nitrogen, and creatinine
SARS-CoV-2:	
 SARS-CoV-2 serology (antibody) will include N protein for prevaccination and postvaccination timepoints. SARS-CoV-2 RT-PCR (nasopharyngeal or mid-turbinate swab)
HIV/HBV/HCV	
 Hepatitis B surface antigen test HIV 4th generation antigen/Ab test Anti-HCV Ab test (and RNA test if anti-HCV Ab positive)
Other analyses:	
Female participants of childbearing potential:
 
 β-human chorionic gonadotropin (serum test at screening; urine test at additional time points) Serum FSH, to confirm postmenopausal status

Individual safety laboratory measurements for hematology, chemistry and coagulation laboratory panel will be provided. All listings will include the cohort, study vaccine, participants ID, laboratory test name result, date and time of measurements, reference range, and flag for measurements that are outside the reference range and sorted by age group, dose group and participant number.

Laboratory abnormalities will be graded for severity using the FDA toxicity grading table (DHHS 2007). Clinically relevant laboratory abnormalities will be reported as AEs using the AE grading.

A summary of patients with an abnormal laboratory value after study vacation (up to Day 8) will be presented. An abnormal laboratory is defined as any value outside of the normal range.

A by-participant listing will be provided for pregnancy test by age group, dose group and participant number.

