9.3 Vital Sign Measurements

Vital sign measurements will include systolic and diastolic blood pressure, pulse rate, respiratory rate, and body temperature. Observed values and changes from baseline will be summarized for each vital sign parameter by time point, and dose group.

A supporting by-participant listing of vital sign parameters along with the investigator assessment will be provided by age group, dose group and participant number.

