15.1 Schedule of Events

	Screening ^a	D1	D4	D8	D15	D29	D91	D181 (EOS)	ET Visit	Unscheduled Visit for Suspected COVID19	Unscheduled COVID-19 Convalescent Visit
Window	D-14 to -1	0	±1	±1	±3	±3	±5	±7	NA	NA	NA
Visit	1	2	Phone	3	4	5	6	7	NA	NA	NA
Informed consent	X										
Inclusion/exclusion	X										
Reassess study vaccine eligibility ^b		X									
Demographics	X										
Medical history (including vaccination history)	X										
Pregnancy test ^c	X	X									
CCI											
Physical examination ^f	X	X		X	X	X	X	X	X	X	X
Vital sign measurements ^g	X	X		X	X	X	X	X	X	X	X
Viral screening assays ^h	X										
Hematology and serum chemistry ^h	X	X ^d		X							
CCI											
Group assignment for Part A/ Randomization for Part B		X									
CCI											
Initiate eDiary for solicited AEs ⁱ		X									
12-lead ECG examination	X			X							
Site staff review of eDiary			X	X							
CCI											
COVID-19 assessment ^k									X ^k	X ^k	

Note: Due to the ongoing pandemic, follow-up visits may be completed via telephone calls, consistent with local regulations.

- a. If the investigator believes there is a reasonable justification to do so, all screening procedures may be repeated (maximum 1 rescreening per participant is allowed). Only results from the rescreening visit, if it occurs, will be taken into consideration and recorded in the eCRF. The participant can only be vaccinated once the investigator receives the results and confirms the eligibility criteria.
- b. Prior to study vaccine administration, participants will be reassessed for development of any new condition that would be considered exclusionary including acute illness or pregnancy. Assessment will be based on pregnancy test results, participant-reported symptomology, vital sign measurements, and physical examination findings.
- c. A serum pregnancy test will be performed at screening in WOCBP. A urine pregnancy test by dipstick will be performed prior to study vaccination. Negative confirmation is required prior to study vaccine administration. Pregnancy test may be repeated at an unscheduled visit per investigator's discretion.
- d. On day 1, the blood sample should be collected *before* study vaccine administration.
- e. **CCI**
[REDACTED]
- f. A complete physical examination including height and weight will be performed at screening. Symptom-directed physical examinations will be performed as clinically indicated at subsequent visits.

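### The primary laboratory percentage counts every out-of-range value after vaccination, so unchanged pre-existing abnormalities are mixed with new ones (minor; affects interpretation only)

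*SAP*

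**What the plan says.** SAP 2.1 lists as a primary endpoint: "Percentage of participants with each abnormal clinical safety laboratory finding for 8 days after study vaccination". SAP 8.1.1 computes the laboratory percentage by dose group over day 1-8. SAP 9.2 then plans a summary of participants with an abnormal value after vaccination, up to Day 8, and supplies the only definition: "An abnormal laboratory is defined as any value outside of the normal range".

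The pieces needed for a baseline comparison exist but are not used here:

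- SAP section 4: "Baseline will be defined as the last non-missing evaluation prior to study vaccine administration".
- SAP 15.1, footnote d: "On day 1, the blood sample should be collected *before* study vaccine administration". Hematology and chemistry are scheduled at screening, Day 1 and Day 8, so Day 8 is the only scheduled post-vaccination sample.
- SAP 9.3, for vital signs: "Observed values and changes from baseline will be summarized for each vital sign parameter by time point, and dose group".

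Protocol 4.1.2, exclusion 8, bars new-onset, clinically significant findings of Grade 1 or above, with this exception: "adults with Grade 1 laboratory abnormalities that have been stable for at least 6 months before enrollment may be included in the study".

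On displays, SAP section 4 adds: "All safety data summaries/displays will be provided by dose group. Details will be included in the TLF shell". Those shells are not among the documents.

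**The concern.** A participant who enters with a stable out-of-range value and leaves Day 8 with the same value counts exactly like one whose value was normal before vaccination and abnormal after it. In a controlled trial the comparator arm would carry the same background. This study has none, so each participant's own baseline is the only direct reference. Comparing dose groups helps only in part: Part A cohorts are filled sequentially, and each may hold 10 to 20 participants from either age group, so the background rate may differ between doses.

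At stake is what a reader can conclude from one primary safety percentage. Vital signs get a change from baseline in the SAP text; the laboratory endpoint, which is primary, does not.

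**Working it through.** **Plan's own figures.** The plan states no rate for this endpoint. Its sample-size arithmetic does reproduce: 1 − 0.95^30 = 78.5% and 1 − 0.90^30 = 95.8%. The same arithmetic applies to background. If 5% of participants carried an unchanged out-of-range value for one analyte, a cohort of 30 would have a 78.5% chance of at least one flag with no vaccine effect.

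**Inputs.** From the documents: 30 per Part A cohort (SAP 4.1) and the any-out-of-range rule (SAP 9.2). Assumed: reference limits covering 95% (±1.96 SD), no vaccine effect, and equal correlation ρ between a person's screening, Day 1 and Day 8 values of 0.5, 0.7 or 0.9.

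**Formulas.** Write each value as √ρ·Z + √(1−ρ)·e, with Z and e standard normal. Let a(Z) be the chance of being in range given Z:

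a(Z) = Φ[(1.96 − √ρ·Z)/√(1−ρ)] − Φ[(−1.96 − √ρ·Z)/√(1−ρ)], with E[a] = 0.95.

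- Case A, entry unselected on laboratory range: flagged = 0.05; newly out = E[a(1−a)].
- Case B, everyone in range at screening: flagged = E[a(1−a)]/0.95; newly out = E[a²(1−a)]/0.95.
- In both, the share already out at baseline = 1 − newly out/flagged.

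| Case | ρ | Flagged | Newly out | Already out, share of flagged | Flagged, of 30 | Newly out, of 30 | Already out, of 30 |
|---|---|---|---|---|---|---|---|
| A | 0.5 | 5.0% | 4.07% | 18.5% | 1.50 | 1.22 | 0.28 |
| A | 0.7 | 5.0% | 3.35% | 33.1% | 1.50 | 1.00 | 0.50 |
| A | 0.9 | 5.0% | 2.04% | 59.3% | 1.50 | 0.61 | 0.89 |
| B | 0.5 | 4.29% | 3.65% | 14.8% | 1.29 | 1.10 | 0.19 |
| B | 0.7 | 3.52% | 2.71% | 23.0% | 1.06 | 0.81 | 0.24 |
| B | 0.9 | 2.14% | 1.40% | 34.7% | 0.64 | 0.42 | 0.22 |

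As a check, flagged in case B is newly out in case A divided by 0.95: 0.0407/0.95 = 0.0429 at ρ = 0.5.

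**Higher background.** Let b be the proportion with an unchanged abnormality and i the proportion newly abnormal among the rest. The SAP count is b + (1−b)i; the new-only count is (1−b)i. With assumed b = 10% and i = 5%, these are 0.10 + 0.90 × 0.05 = 14.5% and 4.5%, or 4.4 against 1.4 of 30. The excess is then 30 × 0.10 = 3 participants per analyte.

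**The case against.** The strongest reply is that the SAP does what the protocol asks: the endpoint is abnormal findings, and the SAP defines and reports them. Nothing is tested, and no escalation or holding rule uses this percentage. That stands.

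Other routes also capture deterioration. Protocol 6.1 has abnormal results recorded as adverse events, naming both those that worsen from baseline and those judged clinically significant. Protocol 6.1.1.3 keeps undeteriorated pre-existing conditions out of adverse events. SAP 9.1.5 tabulates unsolicited events to Day 28. Holding rule 2a covers clinically relevant laboratory abnormalities, Protocol Appendix 5 has Grade 4 abnormalities reported as SAEs, and the SAP 9.2 listings carry dates, values, ranges and flags. This is real but partial cover. Protocol 6.1.4, Appendix 5 and SAP 9.2 tie reporting of abnormalities below Grade 4 to clinical relevance, which is a judgment, and none of these routes changes the reported percentage.

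Three stronger readings are tempting, and the documents do not support them:

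- A reader might infer that safety decisions are compromised. They do not run through this percentage.
- A reader might infer that no baseline split will be produced. The unseen TLF shells could contain one; the point is confined to the SAP text.
- A reader might infer that exclusion 8 places the trial between cases A and B. It works by grade, novelty and clinical significance, not by the laboratory's range. The study also enrols medically stable people, adults of 65 and over, and BMI up to 40, so background rates for some analytes could exceed case A.

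**Conclusion.** The point holds as a minor one. As the SAP is written, the primary laboratory percentage combines unchanged pre-existing abnormalities with new ones and cannot show how many arose after vaccination. In the modelled cases the pre-existing part is about 15% to 59% of flagged participants, but at most 0.89 of 30 per analyte.

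Those figures rest on assumed reference limits, correlations and absence of vaccine effect. The documents give no rates and set no upper bound, and higher baseline rates would enlarge the excess. A baseline comparison removes the pre-existing part only; values that cross a limit by chance remain.

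**What to change.** Keep the existing percentage and the endpoint unchanged. In SAP 8.1.1 and 9.2 add, per analyte and by dose group (and by age group where useful):

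1. A baseline-to-Day 8 shift table of low, normal and high against the laboratory's range.
2. The percentage newly out of range: out of range after vaccination in a direction, low or high, in which the section 4 baseline was not.

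Show FDA grade shifts separately and descriptively where Protocol Table 13-4 has a grade, and report its hemoglobin change-from-baseline rows on their own. A grade change alone should not count as worsening in two situations:

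- The value lies within the laboratory's range. For example, Table 13-4 grades a WBC of 10,900, which a laboratory with an assumed upper limit of 11,000 would call normal.
- A bilirubin grade moves only because liver-test status changed. An unchanged 1.4 × ULN is Grade 1 when liver tests are normal and Grade 2 when any is raised.

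State that only post-vaccination values enter, since the day 1-8 window in SAP 8.1.1 could be read to include the pre-dose Day 1 sample. Use as denominator Safety Set participants with both a baseline and a post-vaccination value.

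The cost is SAP wording and modest programming, with no new samples or visits. The drawback is small cells: 16 analytes across up to 12 dose-by-age groups, some with as few as 10 participants.

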9.3 Vital Sign Measurements

Vital sign measurements will include systolic and diastolic blood pressure, pulse rate, respiratory rate, and body temperature. Observed values and changes from baseline will be summarized for each vital sign parameter by time point, and dose group.

A supporting by-participant listing of vital sign parameters along with the investigator assessment will be provided by age group, dose group and participant number.

9.4 Physical Examination

A complete physical examination including height and weight will be performed at Screening. Symptom-directed physical examinations will be performed as clinically indicated at subsequent visits. The results of the physical examination findings will be listed by participants and dose group, and sorted by age group, dose group and participant number.

9.5 Electrocardiogram

At screening and at the Day 8 visit, all participants will be assessed by 12-lead ECG for evidence of asymptomatic myocarditis or pericarditis. The results of the electrocardiogram findings will be listed by participants and dose group, and sorted by age group, dose group and participant number.

10 Pharmacokinetics

Not applicable.

11 Pharmacodynamics

Not applicable.

12 Interim Analysis

There are 2 planned interim analyses of safety and immunogenicity data for at least neutralizing Ab titers against SARS-CoV-2 WT, Omicron BA.1 or BA.5 variant pseudoviruses. A first interim analysis of safety and immunogenicity data covering at least neutralizing Ab titers against pseudovirus bearing S protein from WT, Omicron BA.1 or BA.5 SARS-CoV-2 up to 14 days after study vaccine administration in participants enrolled in Cohorts 1, 2, and 3 will be performed including at least day 1 and day 15 data. A second interim analysis of safety and immunogenicity data covering at least neutralizing Ab titers against pseudovirus bearing S protein from WT, Omicron BA.1, or BA.5 SARS-CoV-2 will be performed 14 days after participants in Cohorts 4 and 5 have received study vaccine including at least day 1 and day 15 data in Cohorts 4 and 5 and day 29 data in addition in Cohorts 1,2 and 3.

Further to the above the first interim will be based on the PNA data. Available binding IgG data at the time of the first interim will be included, but it is not requested to have 100% of these data at the time of the first interim analysis. For PNA, BA.1, BA.5 and Wuhan (ancestral strain, comparator with CV2CoV) will be prioritized (priority #1). BA.2 can be done as priority #2. Regarding cohort 6 and 7 (lowest doses), it is unsure at this stage whether these cohorts will be enrolled as it will depend on the data generated at 12 mcg.

The safety set will be used for the interim immunogenicity analyses.

13 Changes in the Planned Analysis

Because the assays are not fully validated values below LLOQ or above ULOQ they will be used as released. Results released as below a value will be assigned 0.5*the value. Results released as above a value will be assigned the value.

14 References

